	
Medications which in the opinion of the PI, and in conjunction with the medical monitor, may be expected to significantly interfere with the metabolism or excretion of sodium nitroprusside, and/or may be associated with a significant drug interaction with sodium nitroprusside that may pose a significant risk to subjects' health and/or confound the study data.
 
Pregnant or breast-feeding patients. Women of childbearing potential must have a negative pregnancy test performed at screening visit prior to randomization and prior to baseline at visits 3 and 6. Women enrolled in this trial must use adequate birth control.
 
Subjects with a current (within the last 3 months) DSM-IV-TR diagnosis of alcohol or substance use disorder or dependence (excluding nicotine) as established by the clinical assessment (SCID) at the screening visit (Visit 1) will be excluded.
 
Has tested positive for any of the following: cannabis, opioids, cocaine, amphetamines, barbiturates methadone, methamphetamine and phencyclidine at the screening or baseline visits. If positive, the urine drug toxicology screen may be repeated once based on investigator judgment, but due to safety concerns, the result must be negative for the subject to continue in the study.
 
Subjects at imminent risk of suicide or injury to self or others or history of significant suicide attempt within the last 12 months as measured by the Columbia Suicide Severity Rating Scale (C-SSRS) together with the opinion of the trial investigator.
 
Subjects that have taken an investigational drug or taken part in a clinical trial within 30 days prior to screening.
 
In the opinion of the investigator, participation for any reason would compromise patient safety or integrity of the study

Statistical Methodology	
To test the hypothesis that a statistically significant difference exists in the degree of improvement over 2 weeks between intravenous sodium nitroprusside (0.5 µg/kg/min for 4 hours) and placebo, treatment effect estimates and two-sided 95% confidence intervals (CIs) for sodium nitroprusside and placebo will be provided. A constrained longitudinal data analysis (cLDA) model (Liu et al., 2009) including terms for treatment group, time (as

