and reviewing the SCID, MGH FAST and CGI-S. Pending confirmation of eligibility, the subject will be randomized.

Phase 1:

- Visit 3 (Phase 1 Baseline, Day -2 to -1): Subjects will undergo full battery of study efficacy and safety evaluations. Subjects will also have a urine drug screen, vital signs, 12-lead ECG, and concomitant medications. Visit 4 must occur the day after Visit 3.
- Visit 4 (Phase 1 Study Treatment, Day 0): Anthropometrics, vital signs, concomitant medications, CBC, electrolytes, urinalysis, and urine pregnancy test will be assessed between Hours -1 and 0, before the infusion begins. Randomized i.v. study treatment will be administered from Hours 0 to 4. During these hours there will be safety monitoring (See: Infusion Monitoring and Discharge Procedures). During Hours 5 to 7 following the infusion, there will be a post-infusion debrief, neurological assessment, and assessment of adverse events. Should an infusion room be unavailable on Day 0, the infusion may be scheduled one day before or one day after with prior notification provided to CTNI.

- Visit 5 (Phase 1 Follow-up, Day 7): Subjects will undergo full battery of study efficacy and safety evaluations. Subjects will also have vital signs, 12-lead ECG, and concomitant medications.

Phase 2:

- Visit 6 (Phase 2, Day 13): Subjects will undergo full battery of study efficacy and safety evaluations. Subjects will also have urine drug screen, vital signs, 12-lead ECG, and concomitant medications. Visit 7 must occur the day after Visit 6.
- Visit 7 (Phase 2 Study Treatment Day 14): Anthropometrics, vital signs, concomitant medications, CBC, electrolytes, urinalysis, and urine pregnancy will be assessed between Hours -1 and 0, before the infusion begins. Randomized i.v. study treatment will be administered from Hours 0 to 4. During these hours there will be safety monitoring (See: Infusion Monitoring and Discharge Procedures). During Hours 5 to 7 following the infusion, there will be a post-infusion debrief, neurological assessment, and assessment of adverse events. Should an infusion room be unavailable on Day 7, the infusion may be scheduled one day before or one day after with prior notification provided to CTNI.
- Visit 8 (Phase 2 Follow-up, Day 21): Subjects will undergo full battery of study efficacy and safety evaluations. Subjects will also have vital signs, 12-lead ECG, and concomitant medications.

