The study will be conducted at approximately 4 centers within the USA, including hospitals and outpatient psychiatric clinics. A 20% discontinuation rate is anticipated for this SPCD study, thus, a total of 60 subjects will be initially randomized to have at least 48 subjects complete the study. To account for potential screen failures, up to 100 subjects may be consented in order to randomize 60 subjects total.

Subject Eligibility

Inclusion Criteria

Each subject must meet all of the following criteria to be eligible for this study:

1. Males or Females aged 18-65 years inclusive.
2. Primary diagnosis of Schizophrenia established by a structured psychiatric evaluation (SCID) based on Diagnostic and Statistical Manual of Mental Disorders Forth Edition (DSM-IV-TR) criteria.
3. Written informed consent in compliance with 21 CFR part 50 and in accordance with the International Conference on Harmonization (ICH) Good Clinical Practice (GCP) Guidelines.
4. A Positive and Negative Syndrome Scale (PANSS) (Kay et al., 1994) total score ≥ 70 with a score of ≥ 4 on two or more of the following PANSS items: delusions, conceptual disorganization, hallucinatory behavior, suspiciousness, and unusual thought content.
5. A score of ≥ 4 on the Clinical Global Impression—Severity (CGI-S) (Guy, 1976).
6. Confirmation of both diagnosis and severity of psychosis symptoms by an independent MGH SAFER interview.

7. Must have ongoing antipsychotic treatment for at least 8 weeks, with a stable dose for at least 4 weeks. Subjects who have failed to achieve clinically-recognized symptom reduction to at least 1 marketed antipsychotic agent, given at a Physician Desk Reference (PDR)-defined therapeutic dose for \geq 8 weeks during the past 12 months, as assessed by the MGH FAST, will be eligible
8. Understands and is able, willing, and (in the opinion of the investigator) likely to fully comply with the study procedures and restrictions.

Exclusion Criteria

Subjects who meet any of the following criteria will be excluded from the study.

1. Subjects with a history of renal insufficiency, congestive heart failure, cardiac arrhythmias or history of myocardial infarction.
2. Subjects with a history of symptomatic orthostatic hypotension defined as sitting to standing systolic blood pressure \leq 90mmHg or diastolic blood pressure \leq 60mm Hg with any of the following symptoms: lightheaded or dizzy upon standing, blurry vision, weakness, fainting (syncope), confusion, or nausea.

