3. Subjects with any clinically significant abnormalities as determined by medical history, physical exam, clinical and lab evaluation suggestive of an underlying disease state that may, in the opinion of the investigator, confound the results of study, increase risk to the subject, or lead to difficulty complying with the protocol.
4. Subjects on chlorpromazine, PDE-5 inhibitors, nitrites and any medication with CNS effects with the exception of antipsychotic drugs (other than chlorpromazine) anticholinergics, b-adrenergic antagonists, amantadine, biperiden, diphenhydramine, lorazepam, zolpidem, and temazepam.
5. Medications which in the opinion of the PI, and in conjunction with the medical monitor, may be expected to significantly interfere with the metabolism or excretion of sodium nitroprusside, and/or may be associated with a significant drug interaction with sodium nitroprusside that may pose a significant risk to subjects' health and/or confound the study data.
6. Pregnant or breast-feeding patients. Women of childbearing potential must have a negative pregnancy test performed at screening visit prior to randomization and prior to baseline at visits 3 and 6. Women enrolled in this trial must use adequate birth control.
7. Subjects with a current (within the last 3 months) DSM-IV-TR diagnosis of alcohol or substance use disorder or dependence (excluding nicotine) as established by the clinical assessment (SCID) at the screening visit will be excluded.
8. Has tested positive for any of the following: cannabis, opioids, cocaine, amphetamines, barbiturates methadone, methamphetamine and phencyclidine at the screening or baseline visits. If positive, the urine drug toxicology screen may be repeated once based on investigator judgment, but due to safety concerns, the result must be negative for the subject to continue in the study.

9. Subjects at imminent risk of suicide or injury to self or others, as per the opinion of the investigator, or history of significant suicide attempt within the last 6 months as per C-SSRS.
10. Subjects that have taken an investigational drug or taken part in a clinical trial within 30 days prior to screening.
11. Any other reason that, in the opinion of the investigator, would compromise patient safety or integrity of the study

Table 1- Exclusionary Safety Values of Potential Clinical Concern

Hematology	
Leukocytes	<2 or >17.5 x 10 ³ /mm ³
Platelets	<75 or >700 x 10 ³ /mm ³
Comprehensive Metabolic Panel	

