Sodium	<1.1 times the lower limit or >1.1 times upper limit of the reference range
Potassium	<1.1 times the lower limit or >1.1 times upper limit of the reference range
Chloride	<1.1 times the lower limit or >1.1 times upper limit of the reference range
Carbon Dioxide (Bicarbonate)	<1.1 times the lower limit or >1.1 times upper limit of the reference range
Glucose	>2 times the limits of the reference range
Blood Urea Nitrogen (BUN)	>1.3 times upper limit of the reference range
Creatinine	>1.3 times upper limit of the reference range
Calculated Glomerular Filtration	< 60
Total bilirubin	>2 times the upper limit of the reference range
Aspartate amino transferase (AST)	>3 times upper limit of the reference range
Alanine amino transferase (ALT)	>3 times upper limit of the reference range
Alkaline phosphatase (ALP)	>3 times upper limit of the reference range
Creatine phosphokinase (CPK)	>3 times the upper limit of the reference range
Creatine kinase (CK)	>3 times the upper limit of the reference range
Thyroid Stimulating Hormone (TSH)	>1.5 times upper limit of the reference range
Uric acid	>1.5 times upper limit of the reference range
Lipid panel (triglycerides, total cholesterol (C), HDL-C, calculated LDL-C)	>3 times the upper limit of the reference range

Pregnancy

Serum beta human chorionic gonadotropin (Beta- hCG)	< 6 IU/L negative
---	-------------------

Urine Screen for Drugs of Abuse

Per Exclusionary Criteria #6, a subject is excluded from the study if they meet DSM-IV-TR criteria for diagnosis of alcohol or substance use disorder or dependence (excluding nicotine) within the last 3 months as established by the SCID at the Visit 1 (screening). Per exclusionary criterion 8, for all subsequent urine drug screens (performed at Visits 3 and 6) any individual testing positive for a potential drug of abuse without a documented prescription for that medication will be evaluated by the investigator who will determine if the subject should be terminated from the study due to concerns with respect to subject safety and/or confounding of study data.

Rationale for the Inclusion/Exclusion Criteria

Eligibility criteria for this study have been carefully considered to ensure the safety of the study subjects and to ensure that the results of the study are meaningful in support of the research objectives.

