Urine drug screen: cannabis, opioids, cocaine, amphetamines, methadone, cannabinoids, barbiturates, benzodiazepines, methamphetamine, and phencyclidine.

Urine Pregnancy Test: urine pregnancy test will be performed in female subjects of childbearing potential using a dipstick urine test at visits 4 and 7.

Laboratory Panels assessed at Visit 1 only:

Serum Pregnancy Test: serum beta human chorionic gonadotropin test for pregnancy in female subjects of childbearing potential and FSH for post-menopausal female subjects will be conducted.

Other: glycosylated hemoglobin (Hb)A1c

Study physicians should mark either “CS” for Clinically Significant or “NCS” for Not Clinically Significant in the margin of the laboratory result source document for items outside the normal range.

12-Lead Electrocardiogram (EGG)

A 12-lead ECG will be taken at following a supine rest for 5 minutes. ECG parameters including the QT interval, Bazett's corrected QT interval (QTcB), and QTcF Fridericia's corrected QT interval (QTcF), pulse rate (PR), and QRS intervals, and heart rate will be recorded. The ECGs will be reviewed by the PI or medically qualified Sub-Investigator to assess any immediate abnormalities. The findings of the ECGs will be marked by the PI or medically qualified Sub-Investigator as normal, abnormal-not clinically significant, or abnormal-clinically significant.

The QTcB and QTcF will be manually calculated and recorded on a worksheet that will serve as the source document. All ECGs that are considered abnormal and clinically significant should be evaluated for a change from baseline and captured as an AE.

If any clinically significant change is noted from screening or an ECG is considered abnormal and clinically significant, it will be reported as an AE and will be appropriately recorded in both the source documents and the eCRF.

Study Instruments

The following instruments will be administered according to the schedule in the Schedule of Events in Appendix 1:

Diagnostic Instruments

Structured Clinical Interview for DSM-IV-TR™ (SCID I/P): The SCID, administered by the clinician, includes modules aimed at diagnosing possible Axis I disorders (First et al, 1996). Questions here are asked exactly as written, and each is based on the individual criteria from DSM-IV-TR™.

Massachusetts General Hospital- Fast Additive Summary of Treatment (FAST) - This questionnaire (Appendix 2) provides an efficient, structured means of capturing

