Randomization: When all of the screening assessments, including the SAFER assessment, have been completed and entered into the CTMS, the subject's status will be moved to eligible and the CTMS will generate a randomization ID for the subject. This ID will be accessible to the site pharmacy and will be used to prepare the corresponding study treatment. Once a subject has been assigned a Randomization ID, they will be identified in the CRF by this Randomization ID for the duration of their study participation. The subject ID should no longer be used.

Phase 1

Visit 3 (Baseline, Day -2 to -1)

The following procedures will be conducted at Visit 3 for all subjects:

- Concomitant Medications
- Vital Signs
- Anthropometrics (height, weight, waist circumference, BMI)
- 12-Lead ECG
- Urine Drug Screen
- PANSS
- CGI-S
- CGI-I
- MATRICS
- UPSA-B
- AE/SAE Assessment
- AIMS
- SAFTEE-SI
- C-SSRS

Visit 4 (Phase 1 Study Treatment, Day 0)

Anthropometrics, vital signs, urinalysis, and concomitant medications will be collected for all subjects at the start of Visit 4 (Hours -1 to 0) prior to initiating the infusion. Subjects

will also have blood sample drawn for chemistry and electrolytes. Female subjects of childbearing potential will have a pregnancy test prior to the infusion. If pregnancy test is positive, subject will not continue with the infusion. Subjects who use tobacco will be provided transdermal nicotine in order to prevent withdrawal symptoms. The nicotine replacement will be based on the number of cigarettes per day (cpd) or tobacco equivalent collected at screening.

- ≥ 15 cpd: 21 mg patch
- 8-15 cpd: 14 mg patch
- 5-8 cpd: 7 mg patch
- <5 cpd: as needed nicotine gum or 2mg lozenges (1 piece every 3-4 hours)

Intravenous sodium nitroprusside or Placebo infusion will take place during Hours 0-4. Cardio-pulmonary monitoring will take place throughout intravenous infusion (see Infusion Monitoring and Discharge Procedures).

Following completion of infusion, the subject will have a post-infusion debrief. The following measurements will also be collected for all subjects between hours 4 and 7:

- Vital Signs
- 12-Lead ECG
- AE/SAE Assessment
- AIMS
- SAFTEE-SI
- PANSS
- CGI-S
- CGI-I

Following the completion of all study assessments, a study psychiatrist or nurse practitioner will perform discharge procedures in order release the subject at the end of the visit.

Visit 5 (Phase 1 Follow Up, Day 7)

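### For a Visit 3 drug-screen positive, the protocol both requires a negative repeat before the subject may continue and leaves termination to the investigator

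*Protocol*

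**What the plan says.** The protocol's Exclusion Criteria (section G) open with a general rule: "Subjects who meet any of the following criteria will be excluded from the study". Criterion 8 covers a positive for any of a list of drugs at the screening or baseline visits. It allows one repeat at the investigator's judgment, "but due to safety concerns, the result must be negative for the subject to continue in the study". The Synopsis carries the same condition.

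Later in section G, the paragraph headed Urine Screen for Drugs of Abuse deals with the screens at Visits 3 and 6 and names criterion 8 as its authority. A subject who is positive without a documented prescription "will be evaluated by the investigator who will determine if the subject should be terminated from the study", on grounds of subject safety, confounding of the data, or both. The paragraph mentions neither the repeat nor the required negative.

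The Study Visit Overview (section F) labels Visit 3 the Phase 1 baseline and says: "Subjects will also have a urine drug screen, vital signs, 12-lead ECG, and concomitant medications. Visit 4 must occur the day after Visit 3". The Study Visit Assessment Schedule (section H) also labels Visit 3 as baseline and lists the drug screen there. Visit 4 is the first infusion. The SAP does not address the drug screen.

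**The concern.** Criterion 8 leaves the investigator one decision, whether to repeat the test. The urine-screen paragraph leaves the investigator a different one, whether the subject stays in the trial. At Visit 3 both apply to the same result.

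The infusion normally follows the next day, so there is little time to resolve the question by query. The criterion that would be bypassed is one the protocol justifies by safety.

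There is also a compliance cost. Table 3 gives enrolling an ineligible subject without a protocol exception as an example of a major violation, and the Per Protocol population drops subjects with major violations. A site that retains a subject under the urine-screen paragraph could find that subject classed as a violator of criterion 8.

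**Working it through.** The protocol states no figure on this point, so the check sets the two rules side by side for one case: a Visit 3 positive for a drug listed in criterion 8, no documented prescription, still positive on repeat.

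| Question | Criterion 8 | Urine-screen paragraph |
|---|---|---|
| Does it cover Visit 3? | Yes, as a baseline visit | Yes, by visit number |
| Repeat test? | One, at the investigator's judgment | Not mentioned |
| Must the result be negative? | Yes | Not mentioned |
| Who decides on continuation? | Fixed by the rule | The investigator |
| Outcome for this case | Cannot continue | May be kept, so may be infused at Visit 4 |

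**Is Visit 3 a baseline visit for this purpose?** Section F uses Visit 4 (Day 0) as baseline when defining PANSS response. But neither section F nor section H lists a drug screen at Visit 4, whereas both list one at Visit 3. The urine-screen paragraph also places it there. The column position of the drug screen in Appendix 1 cannot be read reliably from the extracted table, and nothing here depends on it.

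**Where the rules do not collide.** There is no conflict if the repeat is negative or if the investigator ends participation. Benzodiazepines are on the panel ("Urine drug screen: cannabis, opioids, cocaine, amphetamines, methadone, cannabinoids, barbiturates, benzodiazepines, methamphetamine, and phencyclidine") but not in criterion 8, so discretion there contradicts nothing.

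**Two neighbouring questions the text leaves open.**
- Prescribed drugs. Criterion 8 has no prescription exception, and the urine-screen paragraph is silent on prescribed positives. Opioids are a listed drug, while Appendix 3 permits episodic narcotic analgesics for acute indications, up to 3 days per episode.
- Visit 6. Section F does not call it a baseline, but section H labels it the Phase 2 baseline and criterion 6 speaks of baseline at Visits 3 and 6. Together with the plural in criterion 8, this suggests that Visit 6 is included.

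**Size.** Inputs are 60 randomized and 48 planned completers (Sample Size Determination), and Phase 1 arms of about 20 and 40 (Analysis Populations).
- Screens under both rules: 60 × 1 = up to 60.
- Planned discontinuations: 60 − 48 = 12.
- Uncleared positives at an assumed rate of 0% to 5%: 60 × 0 = 0, to 60 × 0.05 = 3 subjects. Three would be 3/12 = 25% of the planned discontinuations.
- Cost of each subject not infused: 1/20 = 5.0% of the nitroprusside arm, or 1/40 = 2.5% of the placebo arm, in Phase 1.

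The rate is an assumption. The last line measures the price of applying criterion 8, not harm from the conflict.

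**The case against.** The strongest reply is that the urine-screen paragraph presents itself as applying criterion 8 and never says that a subject may go on after an uncleared positive. On that reading the investigator evaluates the first positive, and the required negative still governs the outcome. A careful site could read it so. But the paragraph expressly gives the termination decision to the investigator and omits the condition that would bind that decision. The reading has to be supplied by the site.

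Existing controls also count. The medical monitor reviews eligibility issues, waivers go to the medical monitor and the principal investigator case by case, and major violations must be notified within 24 hours. These make an unnoticed infusion less likely, but they do not say which rule is right.

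A reader might go further and infer that sites would in practice follow the urine-screen paragraph, because the Visit 4 text has a firm stop for pregnancy ("If pregnancy test is positive, subject will not continue with the infusion") and none for drugs. The documents do not support that. The pregnancy test is done at Visit 4, so its stop belongs there. The drug screen is a Visit 3 test, so no stop is expected in the Visit 4 text. Criterion 8 appears in two places, and which text a site would reach for is unknown.

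The documents also describe no specific interaction between nitroprusside and a listed drug. The safety stake rests on criterion 8's own stated reason.

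**Conclusion.** The conflict is real, but narrow. At Visit 3, for a drug listed in criterion 8, with no documented prescription and no negative repeat, one rule excludes the subject and the other lets the investigator keep the subject. A site acting on the second could infuse someone the first excludes on safety grounds.

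Up to 60 screens fall under both rules. How many would be uncleared positives is not stated. The range of 0 to 3 subjects rests wholly on the assumed 0% to 5%, and the true number is probably small.

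Two stronger conclusions do not follow. The conflict does not threaten the primary result: it changes no endpoint, power assumption or analysis rule. Nor is it established for prescribed drugs or for Visit 6, where the text is unclear rather than shown to be contradictory. The correction is still worth making, because one of the two texts must be wrong and the error falls just before an infusion.

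**What to change.** Amend the urine-screen paragraph for Visit 3. A positive for a criterion 8 drug without a documented prescription may be repeated once. The repeat must be negative and read before the Visit 4 infusion starts. Otherwise the subject is not infused. Keep the investigator's discretion for panel drugs outside criterion 8, which means benzodiazepines.

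Allow the one-day window around Day 0 to be used while a repeat is pending, and say so. At present Appendix 1 makes the window subject to the coordinating center's permission, section F mentions it only for an unavailable infusion room, and section F also ties Visit 4 to the day after Visit 3.

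Separately, state in criterion 8 and the Synopsis:
- whether a documented prescription is an exception, and reconcile the answer with the narcotic-analgesic allowance in Appendix 3;
- whether the baseline visits include Visit 6.

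The drafting cost is a few sentences. The operational cost is a repeat turned around in about one day. The trial cost is that a few subjects, already randomized at Visit 2, may go uninfused. They are not replaced (section I) and stay in the ITT population. They are asked back for one final visit that includes a PANSS, but that does not supply the scheduled Phase 1 ratings. Neither document states an imputation method. Criterion 8 as written already implies this loss.
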